6.4 Pre-treatment Analysis Set

The pre-treatment analysis set will include all subjects that enroll in the study.

6.5 Dose Limiting Toxicity (DLT) Analysis Set

The DLT Analysis Set includes all subjects who are DLT evaluable. A subject needs to meet one of the following criteria to be DLT evaluable:

1. The subject experiences a DLT in the DLT evaluation period, OR
2. The subject is removed from treatment for an adverse event/toxicity; OR

3. The subject is removed from treatment for reasons other than an adverse event/toxicity, i.e., disease progression, and the subject has received at least 7 days of the target blinatumomab dose; OR
4. The subject does not experience a DLT and completes DLT evaluation period

The DLT evaluation period will be the entire duration of cycle 1 blinatumomab treatment.

6.6 Safety Analysis Set

Safety endpoints will be analyzed at the Primary Analysis using the Primary Analysis Set and at Final Analysis using the Full Analysis Set.

7. Planned Analyses

The following subsections define the planned analyses for this study.

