10.1.2.2 Primary Analysis Set

The primary analysis set will include the first 30 subjects who received blinatumomab. The primary analysis set will be used for the primary analysis.

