10.2 Sample Size Considerations

This is a single-arm estimation study. It is assumed that an MRD-negative rate of 10% could be observed by chance in this study. Therefore, if the assumed rate of MRD negativity is at least 30%, then the sample size for this study (N = 30) is sufficient to demonstrate that, with 95% confidence, the rate of achieving MRD negativity is greater than 10%. This would also be sufficient to demonstrate evidence of clinical activity.

A table showing the CI for different assumed rates of MRD negativity with a sample size of N = 30 is presented below:

Assumed rate of MRD negativity, n (%)	Lower 95% Confidence Limit (%)	Upper 95% Confidence Limit (%)
8 (26.7)	12.3	45.9
9 (30)	14.7	49.4
11 (36.7)	19.9	56.1
12 (40)	22.7	59.4
14 (46.7)	28.3	65.7

The study will enroll approximately 90 subjects to achieve the desired sample size of 30 subjects who are MRD-positive at the time of enrollment or during the run-in period. As part of the run-in period subjects will be followed by clinic visits at 3, 5, 7, 9 and 12 months and thereafter every 3 months up to 24 months for monitoring of MRD status, it is therefore expected that there could be more than 30 subjects who at some point become MRD-positive before the study ends. Any subject who becomes MRD-positive after the 30 subjects required are treated will still be eligible for treatment with blinatumomab, therefore the final sample size may be higher than 30 subjects.

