10.3.3 Primary Analysis

The objective of the primary analysis is to estimate the primary endpoint, MRD-negative rate at the end of cycle 1 of blinatumomab. All subjects in the treatment period are considered MRD positive, regardless whether the cycle 1 day 1 MRD test results are

positive or negative because these subjects have been tested MRD positive in the run-in period. The primary analysis will be triggered when the first 30 enrolled subjects have had the opportunity to complete cycle 1 of blinatumomab treatment. Any subjects treated beyond the required sample size of 30 subjects will not be part of the primary analysis. The safety and tolerability of blinatumomab will also be assessed at the time of the primary analysis.

At the time of the primary analysis the following will be obtained using the pre-treatment analysis set: estimates of the rate and timing of conversion from MRD-negative to MRD positive, and exploratory endpoints of MRD status by the NGS MRD test in PET-CT negative subjects.

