6.1 Full Analysis Set

The full analysis set will include all subjects who received blinatumomab. Subjects who were treated beyond the required sample size of 30 subjects will be included in this analysis set. The full analysis set will be used for the final analysis.

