6.2 Primary Analysis Set

The primary analysis set will include the first 30 enrolled subjects who received at least 1 dose of blinatumomab. The primary analysis set will be used for the primary analysis.

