9.6 Safety Analyses

9.6.1 Analyses of Primary Safety Endpoint(s)

Table 9-4. Safety Endpoint Summary Table

Endpoint	Primary Summary and Analysis Method (Specify Analysis Set if FAS is Not Used)	Sensitivity Analysis
Adverse Event	The subject incidence of adverse events will be summarized for all treatment-emergent adverse events, serious adverse events, adverse events leading to withdrawal of protocol-specified therapy, and fatal adverse events. Primary Analysis Set at the time of Primary Analysis, and Final Analysis Set at the time of Final Analysis will be used for this analysis	Not applicable
Disease Related Events	Subject incidence of disease related events and fatal disease related events in the blinatumomab treatment period (through the safety follow-up visit) will be tabulated by system organ class and preferred term. Primary analysis set will be used for this analysis and Final Analysis Set at the time of Final Analysis will be used for this analysis	Not applicable
Laboratory Test Results	Shift tables between the worst post-baseline and baseline grades for selected laboratory parameters will be provided. The analyses of selected safety laboratory parameters including immunoglobulins, platelets, and liver parameters will include summary statistics over time. Primary Analysis Set at the time of Primary Analysis, and Final Analysis Set at the time of Final Analysis will be used for this analysis	Not applicable
Vital Signs	The number and percentage of subjects with abnormal changes in systolic blood pressure, diastolic blood pressure and heart rate will be summarized. Primary Analysis Set at the time of Primary Analysis, and Final Analysis Set at the time of Final Analysis will be used for this analysis	Not applicable
Electrocardiogram	summaries and statistical analyses of ECG measurements are not planned	Not applicable

Table 9-4. Safety Endpoint Summary Table

Endpoint	Primary Summary and Analysis Method (Specify Analysis Set if FAS is Not Used)	Sensitivity Analysis
Antibody Formation	The incidence and percentage of subjects who develop anti-blinatumomab antibodies (binding and if positive, neutralizing) at any time may be tabulated. Primary Analysis Set at the time of Primary Analysis, and Final Analysis Set at the time of Final Analysis will be used for this analysis	Not applicable

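### At the primary analysis the adverse event and laboratory tables cover only the first 30 treated subjects, so anyone else dosed before the cut-off is left out of them until the final analysis

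*SAP*

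**What the plan says.** SAP 6.6 assigns the safety sets: "Safety endpoints will be analyzed at the Primary Analysis using the Primary Analysis Set and at Final Analysis using the Full Analysis Set". The Primary Analysis Set is defined in SAP 6.2 ("The primary analysis set will include the first 30 enrolled subjects who received at least 1 dose of blinatumomab") and, slightly differently, in protocol 10.1.2.2 ("The primary analysis set will include the first 30 subjects who received blinatumomab"). Protocol 10.3.3, which also places a safety assessment at this time point, adds: "Any subjects treated beyond the required sample size of 30 subjects will not be part of the primary analysis". SAP 7.3 says the same.

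SAP Table 9-4 repeats the restriction row by row. The adverse event row, which covers treatment-emergent, serious and fatal events and those leading to withdrawal, reads: "Primary Analysis Set at the time of Primary Analysis, and Final Analysis Set at the time of Final Analysis will be used for this analysis". The laboratory row has the same wording, and the disease-related event row is to the same effect. SAP section 6 defines no Final Analysis Set. The set that covers everyone treated is the Full Analysis Set of SAP 6.1: "Subjects who were treated beyond the required sample size of 30 subjects will be included in this analysis set".

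Both documents foresee such subjects. Protocol 10.2 says: "Any subject who becomes MRD-positive after the 30 subjects required are treated will still be eligible for treatment with blinatumomab". SAP 3.2 agrees and notes that the final number may exceed 30.

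The SAP text sections do not all follow Table 9-4. SAP 9.6.4 and 9.6.5 (notable vital sign and weight abnormalities), 9.6.7 (antibodies), 9.6.8 (exposure) and 9.6.10 (concomitant medication) name only the Full Analysis Set.

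**The concern.** The figure of 30 belongs to the efficacy estimate. It fixes the denominator for the MRD-negative rate and protects that estimate from being updated as more subjects convert during run-in. None of this bears on safety, where the usual principle is to report everyone exposed. Protocol 2.6 describes neurologic events and cytokine release syndrome that may be life-threatening, so the first formal safety summary should account for every dosed subject.

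The primary analysis waits until the 30th subject has had the opportunity to complete an 84-day cycle. Subjects in run-in can become MRD-positive and be dosed during that wait. As the plan stands, their post-dose events would be absent from the adverse event tables. An exposure table built under SAP 9.6.8 could count them in the same report.

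**Working it through.** **1. Where 30 comes from.** The plan's own figure is the exact (Clopper-Pearson) 95% interval at N = 30. For 9/30 I get 14.7% to 49.4%, and for 8/30 12.3% to 45.9%, as printed in protocol 10.2 and SAP Table 3-1. The other three rows also reproduce. Changing only the safety set leaves all five intervals as they are.

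**2. How many subjects might be omitted.** The documents give no number. As an illustration, assume 30 subjects are first dosed at a constant rate over 24 to 36 months and that dosing continues at that rate.
- 24 months: (30/24) × (84/30.44) = 3.45 subjects in the 84 days after the 30th first dose, or 3.45/33.45 = 10% of those exposed.
- 36 months: (30/36) × (84/30.44) = 2.30 subjects, or 2.30/32.30 = 7%.

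The steps below use k = 3. If dosing has stopped by then, k = 0 and there is no effect.

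**3. Chance that the omitted subjects have an event.** P = 1 − (1 − p)^k, with k = 3:
- p = 5%: 1 − 0.95³ = 14%
- p = 10%: 1 − 0.90³ = 27%
- p = 20%: 1 − 0.80³ = 49%

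These are upper limits. The formula gives the omitted subjects full follow-up, whereas in this scenario they would be part-way through cycle 1 at the cut.

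**4. Chance that the report misses the event type altogether.** The event must also be absent from the first 30: (1 − p)^30 × [1 − (1 − p)^3].
- p = 5%: 0.2146 × 0.143 = 3.1%
- p = 10%: 0.0424 × 0.271 = 1.1%
- p = 20%: 0.00124 × 0.488 = 0.06%

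For an event seen in nobody, the one-sided 95% upper bound, 1 − 0.05^(1/n), is 9.5% at n = 30 and 8.7% at n = 33.

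**5. Wider range (k assumed, event incidence 5%).**

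| Omitted | Share of treated | At least one event among them | Type missed altogether |
|---|---|---|---|
| 2 | 2/32 = 6% | 10% | 0.2146 × 0.098 = 2% |
| 5 | 5/35 = 14% | 23% | 0.2146 × 0.226 = 5% |
| 10 | 10/40 = 25% | 40% | 0.2146 × 0.401 = 9% |
| 15 | 15/45 = 33% | 54% | 0.2146 × 0.537 = 12% |

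**6. Timing.** Cycle 1 ends on day 84. SAP section 5 and SAP 9.6.2 run the treatment-emergent window to 30 days after the end of treatment. After a full 56-day infusion that is day 56 + 30 = 86, and the safety visit, with its +3-day window, falls on about days 86 to 89. For a 30th subject who completes the infusion, the trigger therefore comes 2 to 5 days before that visit. The final analysis follows the trigger by about 365 − 84 = 281 days, or some 9 months.

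**7. Who the first 30 are.** The protocol wording follows dosing order. The SAP wording can be read as enrolment order among dosed subjects. With a run-in of up to 24 months the two can differ, so the SAP does not settle which subjects would be left out.

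**The case against.** The strongest reply is that little depends on these tables and that later subjects are not unobserved. The Data Review Team evaluates adverse events and DLTs in all subjects, at every 10th subject or every 6 months, whichever comes first (protocol 10.3.2, SAP 7.2). SAEs reach the sponsor within 24 hours (protocol 9.2.2.2). The final analysis includes everyone treated (SAP 7.4). No test or stopping decision uses the primary safety tables. A single set of 30, all with the opportunity to complete cycle 1, also avoids mixing in partly followed subjects whose incidences would be understated.

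All of that stands, and it rules out several stronger readings that a reader might infer:
- That subjects will certainly have been dosed after the 30th by the cut-off. The documents say only that more than 30 could be treated, and enrolment may stop at about 30 assigned.
- That every safety table is confined to 30. The SAP sections naming the Full Analysis Set contradict this, and SAEs before the first dose are summarised for all enrolled subjects (SAP 9.6.2).
- That a death in a 31st subject would go unseen for 9 months. It would be missing from one set of descriptive tables, not from safety oversight.
- That 14%, 27% and 49% are the chances of the report missing an event type. Those chances are the far smaller figures in step 4.
- That the day-84 trigger is a serious flaw. It is a trigger rather than a stated data cut-off, and it touches only the last subject or so.

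What the reply does not do is give a safety reason for the cap. Monitoring does not change what the primary report shows, and partial follow-up can be flagged. The printed DLT boundaries also end at 30 subjects, so none is stated for those treated later.

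**Conclusion.** The point holds in a limited form. SAP 6.6, SAP 7.3 and Table 9-4, with protocol 10.3.3, exclude any subject treated beyond the first 30 from the adverse event, SAE, fatal event, disease-related event and laboratory summaries at the primary analysis. Both documents allow such subjects to exist. Their events are deferred to the final analysis. Separately, Table 9-4 and the SAP text sections name different sets, one of them undefined, so denominators in one report may not agree.

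The size is uncertain and probably modest. The number omitted may be zero. The estimate of about 3 rests on an assumed constant dosing rate, and the event probabilities rest on assumed incidences and full follow-up. This is a change the sponsor should make because it is cheap and removes an inconsistency. It does not cast doubt on the efficacy result or show a gap in safety monitoring.

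**What to change.** - In SAP 6.6, SAP 7.3, SAP Table 9-4 and protocol 10.3.3, state that safety at the primary analysis is summarised in all subjects who received at least one dose by the data cut-off, that is, the Full Analysis Set as of that date. Keep the first-30 set for the MRD-negative rate only.
- Replace Final Analysis Set with Full Analysis Set throughout Table 9-4, and make SAP 9.6.4, 9.6.5, 9.6.7, 9.6.8 and 9.6.10 consistent with it.
- Set the safety data cut-off no earlier than the scheduled safety follow-up visit of the 30th treated subject.
- Align SAP 6.2 with protocol 10.1.2.2 on whether the first 30 are counted by dosing or by enrolment order.

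The cost is wording in two documents. The safety denominator may exceed 30, and the last subjects will have partial follow-up, which can be handled by flagging them or by also showing the first 30. The cut moves by a few days. The efficacy analysis does not change.

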7.1 Interim Analysis and Early Stopping Guidelines

Amgen will conduct evaluations of the ongoing DLT rate to assess if the threshold for early trial termination as defined in section 6.2.2 of protocol amendment 3 dated July 18, 2018 has been reached. The stopping rules will use a Bayesian approach to terminate the study if the posterior probability that the true DLT rate is greater than 25% is > 90%.

Table 7-1. Stopping Boundary With Posterior Probability of 90% and DLT Limit of 25%

Number of DLT evaluable subjects	Stop study if observing these many DLTs
10	≥ 5
20	≥ 8
30	Study completes

Table 7-2. Operating Characteristics With Batch Size of 10 Subjects

True DLT rate	Probability of stopping	Average sample size
0.20	5%	30
0.25	14%	28
0.30	27%	26
0.35	44%	24
0.40	62%	21

7.2 Data Review Team

A Data Review Team (DRT) will review safety data periodically. A DRT is a group, internal to Amgen but external to the relevant blinatumomab product team, that reviews

accumulating data from the ongoing clinical trial to ensure no avoidable increased risk for harm to subjects. Continuous toxicity monitoring for early termination of the trial will be performed with the early stopping boundary defined in [Table 7-1](#). Adverse events and DLTs (as defined in protocol Section 6.2.2) observed in all subjects will be evaluated every 10th subject or every 6 months, whichever occurs earlier. The DRT includes a clinician, a safety physician, and a biostatistician. Membership, procedures, and meeting timing will be described in detail in the study DRT charter.

7.3 Primary Analysis

The objective of the primary analysis is to estimate the primary endpoint, MRD-negative rate at the end of cycle 1 of blinatumomab. The primary analysis will be triggered when the first 30 enrolled subjects have had the opportunity to complete cycle 1 of blinatumomab treatment. Any subjects treated beyond the required sample size of 30 subjects will not be part of the primary analysis.

At the time of the primary analysis, the primary endpoint (MRD-negative rate at end of cycle 1 of blinatumomab) will be analyzed using the Primary Analysis Set. The safety and tolerability of blinatumomab, pre-treatment estimates of the rate and timing of conversion from MRD-negative to MRD-positive, and MRD status by the NGS MRD test in PET-CT negative subjects will also be assessed.

The primary analysis is will be based on a clean and locked database.

7.4 Final Analysis

The main objective of the final analysis is to provide estimates of the secondary and exploratory endpoints. The final analysis will also include updated estimates for the endpoints assessed at the primary analysis (MRD-negative rate and MRD prior to blinatumomab treatment). The updated estimates will include all subjects enrolled in the study who received at least one dose of blinatumomab. This would include any subjects treated after the expected sample size of 30 subjects.

The final analysis will be conducted when the subjects in the Primary Analysis Set have had an opportunity to complete the long-term follow-up visit 1 year from the first dose of blinatumomab. The final analysis will also assess the potential long-term effect of blinatumomab on safety. This will include any subjects treated after the expected sample size of 30 subjects.

For the final analysis, the secondary and exploratory endpoints will be assessed as well as updating the estimates for the endpoints assessed at the primary analysis

(MRD-negative rate and MRD prior to blinatumomab treatment). The Full Analysis Set will be used for the final analysis, which includes any subjects treated after the expected sample size of 30 subjects. Sensitivity analysis will be performed on Target Dose Analysis set.

The final analysis is will be based on a clean and locked database.

8. Data Screening and Acceptance

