10.1.4 Handling of Missing and Incomplete Data

Subjects missing post-baseline MRD assessments will be considered not to have achieved MRD-negative status.

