10.4.2 Primary Efficacy Endpoint

MRD-negative rate at the end of cycle 1 of blinatumomab. MRD is defined as negative when the tumor clone sequence in plasma is below the assay's limit of detection (to be determined in the assay validation).

MRD-negative rate is calculated as the number of subjects with MRD-negative status after treatment with blinatumomab divided by the total number of subjects in the respective analysis set.

Exact binomial 95% CI will be used to analyze MRD-negative rate.

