3.2 Sample Size

This is a single-arm estimation study. It is anticipated that an MRD negative rate of 10% could be observed by chance in this study. Therefore, if the observed rate of MRD negativity is at least 30%, then the sample size for this study ($N = 30$) is sufficient to demonstrate that, with 95% confidence, the rate of achieving MRD negativity is greater than 10%. This would also be sufficient to demonstrate evidence of clinical activity.

A table showing the exact binomial confidence intervals for different observed rates of MRD negativity with a sample size of $N = 30$ is presented below:

Table 3-1. Confidence Intervals for Different Observed Rates of MRD Negativity With a Sample Size of 30

Observed rate of MRD negativity, n (%)	Lower 95% Confidence Limit (%)	Upper 95% Confidence Limit (%)
8 (26.7)	12.3	45.9
9 (30.0)	14.7	49.4
11 (36.7)	19.9	56.1
12 (40.0)	22.7	59.4
14 (46.7)	28.3	65.7

The study will enroll approximately 90 subjects to achieve the desired sample size of 30 subjects who are MRD positive at the time of enrollment or during the run-in period. As part of the run-in period, subjects will be followed by clinic visits at 3, 5, 7, 9 and 12 months and thereafter every 3 months up to 24 months for monitoring of MRD status, thus it could be more than 30 subjects who at some point become MRD positive before the study ends. Any subject who becomes MRD positive after the first 30 subjects with treatment of blinatumomab will still be eligible for treatment and included in Full Analysis Set. Therefore the final sample size may be higher than 30 subjects.

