4.2 Subgroups

Analysis of primary and secondary endpoints in the subgroups defined by the above baseline covariates will be explored, if appropriate, depending on the sample size.

5. Definitions

Age-adjusted international prognostic index (aalPI)

aalPI score will be derived by assigning one point to each of the risk factors: disease stage III/IV, elevated LDH level and ECOG score ≥ 2 (please refer to Appendix D of the protocol).

Age at enrollment

Subject age at enrollment will be collected in years in the clinical database.

Baseline

Unless otherwise specified the baseline value for parameters/assessments scheduled to be performed on the same day as the first administration of blinatumomab, is the last value measured before the first administration of blinatumomab on that day. For parameters/assessments not scheduled to be performed (or scheduled but not performed) on the same day as the first administration of blinatumomab, the baseline value is the value measured closest to the day of first administration of blinatumomab.

Cumulative dose of investigational product (blinatumomab)

The cumulative dose in μg is defined as the following with summation over infusions:

\sum (duration of infusion [days] for each dose received x dose received [μg]). Cumulative dose will be calculated within blinatumomab cycle 1.

Death date

For subjects who die during the study, the death date will be recorded on the event, end of study and/or survival status eCRF. The earliest death date will be used for analysis if the dates are inconsistent among these CRF pages. For deaths collected after a subject has ended study (eg, through public records), the death date will be recorded on the long-term follow-up.

Duration of blinatumomab treatment

For each infusion episode within cycle 1, the duration of exposure to blinatumomab will be calculated by subtracting the start date and time from the stop date and time. If either a start or stop time is missing, only the date portion will be used in calculating the duration of a specific infusion. The duration will be the sum of the individual infusion durations within cycle 1. The duration will be rounded to the nearest day.

Duration of MRD-negative status

The duration of MRD-negative status will be assessed only in subjects who achieve MRD-negative status after blinatumomab treatment. Subjects missing post-baseline MRD assessments will be considered not to have achieved MRD negative status.

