On and after study day 1: study day= (date - date of Study Day 1) + 1

Treatment-emergent adverse event (TEAE)

Adverse events (AEs) starting on or after first dose of protocol-specified therapy as determined by the flag indicating if the adverse event started prior to the first dose on the Adverse Events Summary CRF and up to and including 30 days after the end of protocol-specified therapy. This reporting window also applies to treatment-emergent serious adverse events (SAEs).

Treatment-emergent disease-related event

Events categorized as Disease-related Events (DREs) starting on or after first dose of blinatumomab as determined by the flag indicating if the event started prior to the first dose on the Events CRF and up to and including 30 days after the end of blinatumomab.

Disease Related Events

Subject incidence of disease related events and fatal disease related events in the blinatumomab treatment period (through the safety follow-up visit) will be tabulated by

system organ class and preferred term. Refer Protocol section 9.1.1 for more details on disease related events by their system organ class.

Triple hit

Triple hit is defined as the positive rearrangement of c-MYC, BCL2 and BCL6 as collected on the 'Disease-Specific Features on the DLBCL Disease History (COO)' eCRF page.

6. Analysis Sets

This study will define the following analysis sets for the purpose of statistical analysis: Full Analysis set, Primary analysis Set, Target Dose Analysis Set, Pre-treatment Analysis Set and Dose Limiting Toxicity (DLT) Analysis Set.

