9.5 Efficacy Analyses

Table 9-1. Primary Efficacy Endpoint Summary Table

Endpoint	Primary Summary and Analysis Method	Sensitivity Analysis
Proportion of subjects who achieve MRD response (MRD negativity) after cycle 1 of blinatumomab. MRD negativity is determined as the best MRD response on day 57 or day 71(+3 days) via MRD testing.	The MRD-negative rate at the end of cycle 1 of blinatumomab is calculated as the number of subjects with MRD-negative status after treatment with blinatumomab divided by the total number of subjects in the Primary Analysis Set for Primary Analysis. Exact binomial 95% CI will be summarized. The Full Analysis Set will be used at final analysis..	A sensitivity analysis will be performed using the Target Dose Analysis Set for the final analysis.

Table 9-2. Secondary Efficacy Endpoint Summary Table

Endpoint	Primary Summary and Analysis Method	Sensitivity Analysis
PFS	Kaplan-Meier (KM) analyses (KM plot and KM estimates) on the Full Analysis Set.	A sensitivity analysis will be performed using the Target Dose Analysis Set for the final analysis
Duration of MRD-negative status	Kaplan-Meier (KM) analyses (KM plot and KM estimates) on the Full Analysis Set.	A sensitivity analysis will be performed using the Target Dose Analysis Set for the final analysis
OS	Kaplan-Meier (KM) analyses (KM plot and KM estimates) on the Full Analysis Set.	A sensitivity analysis will be performed using the Target Dose Analysis Set for the final analysis.

Secondary efficacy endpoints will be assessed only at final analysis.

Table 9-3. Exploratory Efficacy Endpoint Summary Table

Endpoint	Primary Summary and Analysis Method	Sensitivity Analysis
MRD-negative rate	The MRD-negative rate will be summarized at each time point measured following blinatumomab treatment using both Primary and Full Analysis Sets.	A sensitivity analysis will be performed using the Target Dose Analysis Set for the final analysis
Incidence of alloHsCT	Incidence of alloHsCT (number of subjects with alloHsCT), including the methodology (Intensity of Conditioning Regimen and Donor Type) and clinical outcomes (Maximum grade of aGVHD) will be summarized using Full Analysis Set.	A sensitivity analysis will be performed using the Target Dose Analysis Set for the final analysis

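### The final MRD-negative rate has no minimum follow-up for subjects treated after the first 30, which can only bias it downward (probably slightly), and the SAP names two analysis sets for the final run-in MRD endpoints

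*SAP*

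**What the plan says.** **Final MRD-negative rate.** SAP 7.4 sets the timing: "The final analysis will be conducted when the subjects in the Primary Analysis Set have had an opportunity to complete the long-term follow-up visit" at one year from first dose. The same section sets the population for the updated MRD estimates: "The updated estimates will include all subjects enrolled in the study who received at least one dose of blinatumomab". Protocol 10.3.4 agrees on both. Treatment does not stop at 30. Under SAP 3.2 a subject who converts later "will still be eligible for treatment and included in Full Analysis Set". Run-in lasts up to 24 months, so such conversions can continue after the 30th first dose.

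Protocol 10.4.2 defines the rate as MRD-negative subjects "divided by the total number of subjects in the respective analysis set", and SAP Table 9-1 adds: "The Full Analysis Set will be used at final analysis". Table 9-1 takes response as the best result on day 57 or day 71 (+3 days). On missing data, protocol 10.1.4 says: "Subjects missing post-baseline MRD assessments will be considered not to have achieved MRD-negative status". The SAP repeats that rule only in section 5, under duration of MRD-negative status.

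The primary analysis (SAP 7.3) waits until the first 30 subjects have had the chance to complete cycle 1. The final update has no such condition for later subjects.

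**Run-in MRD endpoints.** SAP 7.4 lists MRD before blinatumomab among the estimates to be updated in treated subjects, using the Full Analysis Set. The closing line of Table 9-3 also gives the Full Analysis Set for exploratory efficacy endpoints at the final analysis. The two Table 9-3 rows for these endpoints, and SAP 9.5.3, give the Pre-treatment Analysis Set, which SAP 6.4 defines as everyone enrolled. The sensitivity column for both rows names the Target Dose Analysis Set.

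**The concern.** A response rate needs a denominator of people who could have responded. The plan applies that principle to the first 30 subjects at the primary analysis but not to the extra subjects who enter the final update. Anyone dosed shortly before the cut adds one to the denominator and nothing to the numerator, so the error runs in one direction.

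The run-in problem is a contradiction about who is counted. Part 2 eligibility (protocol 4.2.1, criterion 112) requires an MRD-positive result, so everyone treated has been positive. An ever-positive percentage among treated subjects describes the entry criterion and says nothing about how often PET-CT negative patients become positive after transplant. Two programmers, each following a different passage, would report different results for the same endpoint.

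**Working it through.** **1. The plan's own figure.** The two-sided 95% Clopper-Pearson interval for 9/30 is 14.7% to 49.4%, as in SAP Table 3-1. The other four rows of that table also reproduce.

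**2. When a subject becomes testable.** From first dose onward SAP section 5 sets "study day= (date - date of Study Day 1) + 1". Day 57 therefore falls 57 − 1 = 56 days after first dose, and day 74 (day 71 + 3) falls 73 days after. A subject dosed under 56 days before the cut has neither qualifying test. One dosed 56 to 72 days before may have only the first. All of the first 30 have had the opportunity for a year of follow-up by the trigger, so only later subjects can be affected.

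**3. Cost per untestable subject.** With true rate p, N treated and k untestable, the expected rate is p(N − k)/N, so the bias is −pk/N. At p = 30% and k = 1:

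| N treated | Bias (points) |
|---|---|
| 31 | −30/31 = −0.97 |
| 40 | −30/40 = −0.75 |
| 45 | −30/45 = −0.67 |

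**4. Effect on a reported result.** Adding untestable subjects to 9/30:

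| Untestable | Rate | Exact 95% CI |
|---|---|---|
| 0 | 9/30 = 30.0% | 14.7–49.4 |
| 1 | 9/31 = 29.0% | 14.2–48.0 |
| 2 | 9/32 = 28.1% | 13.7–46.7 |
| 3 | 9/33 = 27.3% | 13.3–45.5 |

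With 2 of 40 untestable, 11/40 = 27.5% (14.6–43.9) would be reported against 11/38 = 28.9% (15.4–45.9) among testable subjects.

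**5. How many such subjects to expect.** The documents do not give accrual, so this step rests on assumptions, tested by simulation:

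- 90 subjects accrued per 18, 24 or 36 months.
- 10% or 20% positive at screening, and 33.3% or 50% positive by 24 months.
- Truncated-exponential conversion (median parameter 6 or 12 months), detected at the scheduled visits.
- First dose one month after detection, and the cut 12 months after the 30th first dose.
- Runs made without losses, and with 15% failing Part 2 plus 15% run-in dropout.

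Mean bias, counting subjects under 56 days as untestable:

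- **Enrolment fixed at 90, 33.3% positive:** 0.07 to 0.12 points without losses and at most 0.02 with them. Without losses only about half the runs reach 30 treated, and runs with 30 or fewer count as zero bias.
- **Enrolment open until 30 treated, 33.3% positive:** up to about 0.7 points.
- **50% positive:** up to about 1.0 point.

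Treating everyone under 73 days as unable to respond is an upper bound. It gives at most 0.15, about 1.0 and about 1.4 points respectively.

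**6. Run-in endpoints, set against each other at planned numbers.** In the Pre-treatment Analysis Set the ever-positive percentage is 30/90 = 33.3% (23.7–44.1). In treated subjects it is 30/30 = 100% whatever the data. Status at screening and timing of conversion can still be estimated in treated subjects, but only among converters who went on to treatment.

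**The case against.** **Size.** The planning-case bias is about a tenth of a point, against an interval for 9/30 that is roughly 35 points wide. No decision rule uses the final rate. This stands, and it limits the weight of the point. With 9 responders the lower limit would fall below 10% only at 44 treated, that is with 14 untestable subjects.

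**The missing-data rule.** A reader might infer that the plan expressly scores late-dosed subjects as non-responders. The texts do not go that far. Protocol 10.1.4 does not mention visits not yet due. The SAP version ("Subjects missing post-baseline MRD assessments will be considered not to have achieved MRD negative status") sits under the duration endpoint. Days 15 and 43 are also post-baseline tests, so a subject with those results may not be missing in the rule's sense. The dilution comes from the fixed denominator combined with the day 57/71 definition, and it arises however the missing-data rule is read.

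**The cut.** SAP 7.4 gives a trigger and requires a clean, locked database, but gives no cut-off date. SAP 9.2 plans to present the last subject's blinatumomab end and end-of-study dates, which suggests that the sponsor may wait. If every treated subject finishes cycle 1 first, the bias vanishes, but nothing requires that.

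**Mitigation.** The Target Dose sensitivity analysis requires 7 days at the highest dose, which starts on day 15. It therefore drops most subjects dosed under about 21 days before the cut, but not those dosed from then up to 56 days before.

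**Run-in endpoints.** Endpoint-specific text would ordinarily prevail over general sentences, and protocol 10.3.3 uses the pre-treatment set at the primary analysis. That makes the likely intent clear. However, SAP 7.4 names pre-treatment MRD explicitly, so the conflict is real.

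**Conclusion.** Both parts hold, at modest weight.

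The final MRD-negative rate can be biased downward only, by 0.67 to 0.97 points per untestable subject (true rate 30%, 45 down to 31 treated). The expected total is close to nil with 90 enrolled and 30 positive, and about 1 point or less in the wider scenarios, or about 1.4 on the upper bound. The per-subject figures are arithmetic. The totals depend on assumed accrual and conversion. A reader might infer that the primary result is compromised. It is not, because its set and its opportunity condition exclude the problem.

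For the run-in endpoints, the SAP contradicts itself on the final analysis set. A reader might infer that all of these endpoints become meaningless if SAP 7.4 governs. Only the ever-positive percentage is fixed at 100%; screening status and timing remain estimable, in a selected group. On either reading, a Target Dose sensitivity analysis tells nothing about the ever-positive percentage, since that set is drawn from treated subjects. The endpoints are exploratory.

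**What to change.** **Final MRD-negative rate.** Restrict the denominator to Full Analysis Set subjects who had the opportunity to complete cycle 1, that is, first dosed at least 84 days before the data cut. This matches the condition already used in SAP 7.3. Missing day 57 and day 71 tests among these subjects still count as non-response. Make the same edit in SAP 7.4, Table 9-1 and SAP 9.5.1. Record it in SAP section 10 as a change from protocol 10.3.4, because that section now declares no changes.

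**Run-in MRD endpoints.** In SAP 7.4 and the closing line of Table 9-3, state that these endpoints use the Pre-treatment Analysis Set at both the primary and the final analysis. Delete the Target Dose sensitivity entries from the two Table 9-3 rows.

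**Cost.** A few sentences, two deleted table cells and one entry in section 10, with no new data. The downside is a slightly smaller denominator for the final rate than all treated subjects.
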